Placebo 0.15	0.15 ml	Formulation buffer S9b				X		

RSV-Ld: low dose ChAd155-RSV vaccine (5 x 10⁹ vp); **RSV-Md:** middle dose ChAd155-RSV vaccine (1.5 x 10¹⁰ vp); **RSV-Hd:** high dose ChAd155-RSV vaccine (5 x 10¹⁰ vp).

- Control: placebo control (Formulation buffer S9b).
- Vaccination schedule(s): two IM vaccine doses administered according to a 0, 1-month schedule (i.e. at Day 0 and Day 30).
- Treatment allocation: infants will be randomized using a randomization system on internet (SBIR) at first vaccination.
- Blinding: observer-blind in Epoch 001 and single-blind in Epoch 002.

Table 3 Blinding of study epochs

Study Epochs	Blinding
Epoch 001	observer-blind
Epoch 002	single-blind

- Sampling schedule:
 - Blood samples for **biochemistry** will be taken from all infants at Screening (up to 29 days before first vaccination to Day 0) and on Day 30, and Day 60 (refer to [Table 11](#) for the list of parameters to be tested). Blood samples for **hematology** will be taken from all infants at Screening (up to 29 days before first vaccination to Day 0) and on Day 1, Day 30, Day 31, and Day 60 (refer to [Table 11](#) for the list of parameters to be tested). Day 7 hematology testing will be performed if any \geq Grade 1 for platelet decrease is detected on Day 1 after vaccination, to ensure its resolution. Similarly, hematology testing on Day 37 will be performed if any \geq Grade 1 for platelet decrease is detected on Day 31. A clinical examination with special attention given to detection of spontaneous bleeding or easy bruising and evidence of bruising or petechiae will be performed by the investigator/study staff on Day 1, Day 3 and Day 7 after each vaccination (i.e. Day 1, Day 3, Day 7, Day 31, Day 33, and Day 37). The visits on Day 3 and Day 33 may be replaced by a phone call by the investigator/study staff to inquire of the infants' general health and to solicit reports of a rash, spontaneous bleeding or easy bruising. On Day 1, and Day 31, special attention will also be given to the detection of petechiae or evidence of petechiae induced by the tourniquet. This special attention to detection of petechiae or evidence of petechiae induced by the tourniquet will also be given on Day 7 and/or Day 37 in case hematology

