11.8. Analysis of safety

11.8.1. Within groups assessment

The analysis will be performed on the TVC.

The percentage of subjects with at least one **local AE** (solicited and unsolicited), with at least one **general AE** (solicited and unsolicited) and with any AE during the 7-day or 30-day follow-up period will be tabulated with exact 95% CI after each vaccine dose and overall (**Amended 10 December 2017**). The percentage of doses followed by at least one local AE (solicited and unsolicited), by at least one general AE (solicited and unsolicited) and by any AE during the 7-day or 30-day follow-up period will be tabulated, overall vaccination course, with exact 95% CI. The same computations will be done for Grade 3 AEs, for any AEs considered related to vaccination and for any Grade 3 AEs considered related to vaccination.

The percentage of subjects reporting each individual **solicited local AE** (any grade, Grade 2, Grade 3, resulting in a medically attended visit) and **solicited general AE** (any grade, Grade 2, Grade 3, any related, Grade 2 related, Grade 3 related, resulting in medically attended visit) during the 7-day follow-up period (Day 0-6) will be tabulated for each group after each vaccine dose and overall. Similarly, the percentage of doses followed by each individual solicited local and general AE and their sub-categories, will be tabulated, overall vaccination course, with exact 95% CI.

For fever, the number and percentage of subjects reporting fever by half degree (°C) cumulative increments during the 7-day follow-up period (Day 0-6) will be tabulated for each group after each vaccine dose and overall. Similar tabulations will be performed for any fever with a causal relationship to vaccination, Grade 3 (> 39.5°C) causally related fever and for any fever resulting in a medically attended visit. In addition, the prevalence of any and Grade 3 fever will be presented graphically over time after vaccination.

For each group and for each **hematology and biochemistry** parameter:

- The percentage of subjects having hematology and biochemistry results below or above the local laboratory normal ranges will be tabulated by timepoint.

The maximum grading from Screening up to Visit 9 (Day 60) will be tabulated (Refer to [Appendix C](#)).

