## **6.4. Analysis of safety**

### **6.4.1. Analysis of safety planned in the protocol**

#### **6.4.1.1. Within groups assessment**

The analysis will be based on the ES on each treatment groups separately.

The percentage of subjects with at least one local AE (solicited and unsolicited), with at least one general AE (solicited and unsolicited) and with any AE during the 7-day or 30-day follow-up period will be tabulated with exact 95% confidence interval (CI) after each vaccine dose and overall. The percentage of doses followed by at least one local AE (solicited and unsolicited), by at least one general AE (solicited and unsolicited) and by any AE during the 7-day or 30-day follow-up period will be tabulated, overall vaccination course, with exact 95% CI. The same computations will be done for Grade 3 AEs, for any AEs considered related to vaccination and for any Grade 3 AEs considered related to vaccination.

The percentage of subjects reporting each individual solicited local AE (any grade, Grade 2, Grade 3, resulting in a medically attended visit) and solicited general AE (any grade, Grade 2, Grade 3, any related, Grade 2 related, Grade 3 related, resulting in medically attended visit) during the 7-day follow-up period (Day 1-7) will be tabulated for each group after each vaccine dose and overall. Similarly, the percentage of doses followed by each individual solicited local and general AE and their sub-categories, will be tabulated, overall vaccination course, with exact 95% CI.

For fever, the number and percentage of subjects reporting fever by half degree (°C) cumulative increments during the 7-day follow-up period (Day 0-6) will be tabulated for each group after each vaccine dose and overall. Similar tabulations will be performed for any fever with a causal relationship to vaccination, Grade 3 (> 39.5°C) causally related fever and for any fever resulting in a medically attended visit. In addition, the prevalence of any and Grade 3 fever will be presented graphically over time after vaccination.

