### 11.2. Statistical Method References

The exact two-sided 95% CIs for a proportion within a group will be the Clopper-Pearson exact CI [Clopper CJ, Pearson ES. The use of confidence or fiducial limits illustrated in the case of binomial. *Biometrika*. 1934; 26:404-413].

The standardised asymptotic two-sided 95% CI for the group difference in proportions is based on the method described in the following paper: Robert G. Newcombe, interval estimation for the difference between independent proportions: comparison of eleven methods, *Statist Med*. 1998; 17, 873-890]. The standardised asymptotic method used is the method six.

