### 11.3.2. Dose number

- The study dose number is defined in reference to the number of study visits at which vaccination occurred. More specifically dose 1 refers to all vaccines administered at the first vaccination visit while dose 2 corresponds to all vaccinations administered at the second vaccination visit even if this is the first time a product is administered to the subject.
- Relative dose: the relative dose for an event (AE, medication, vaccination) is the most recent study dose given before an event. In case the event takes place on the day a study dose is given, the related dose will be that of the study dose, even if the event actually took place before vaccination. For instance, if an adverse event begins on the day of the study vaccination but prior to administration of the vaccine, it will be assigned to this dose. In case a study dose is not administered and an event occurs after the subsequent study dose (eg 2nd study dose), the relative dose of the event will be study dose associated to the subsequent study dose (eg dose 2).
- The number of doses for a product is the number of times the product was administered to a subject.
- The incidence per dose is the number of vaccination visits at which an event was reported among all vaccination visits.

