**<each group>:**

- RSV-Ld = Low dose ChAd155-RSV vaccine (5 x 10^9 vp)
- RSV-Md = Middle dose ChAd155-RSV vaccine (1.5 x 10^10 vp)
- RSV-Hd = High dose ChAd155-RSV vaccine (5 x 10^10 vp)
- Placebo-Ld = Non-active control (0.5 ml)
- Placebo-Md = Non-active control (0.15 ml)
- Placebo-Hd = Non-active control (0.5 ml)

For each dose:

- N = number of subjects with the corresponding documented dose
- n/% = number/percentage of subjects reporting the type of symptom at least once following the corresponding dose

For Overall/dose:

- N = number of documented dose
- n/% = number/percentage of doses followed by at least one type of symptom

For Overall/subject:

- N = number of subjects with at least one documented dose
- n/% = number/percentage of subjects reporting the type of symptom at least once
- 95%CI= Exact 95% confidence interval; LL = lower limit, UL = upper limit
- The maximum intensity of local injection site redness/swelling was coded as follows:
- 1: > 0.1 mm to < 5 mm
- 2: ≥ 5 mm to ≤ 20 mm
- 3: > 20 mm

**Template 18 Incidence of solicited local symptoms reported during the 7-day (Days 1-7) post-vaccination period following each dose and overall by maximum grading <Exposed Set>**

Dose	Symptom	Type	<each group>				
			N	n	%	LL	UL
DOSE 1	Pain	All					
		Grade 1					
		Grade 2					
		Grade 3					
		Medical advice					
	Redness (mm)	All					
		≥0.1 - <5.0					
		≥5.0 - ≤20.0					
		>20					
		Medical advice					
	Swelling (mm)	All					
		≥0.1 - <5.0					
		≥5.0 - ≤20.0					
		>20					
		Medical advice					
DOSE 2	Pain	All					
		Grade 1					
		Grade 2					
		Grade 3					
		Medical advice					
	Redness (mm)	All					
		≥0.1 - <5.0					
		≥5.0 - ≤20.0					
		>20					
		Medical advice					
	Swelling (mm)	All					
		≥0.1 - <5.0					
		≥5.0 - ≤20.0					
		>20					
		Medical advice					
OVERALL/DOSE	Pain	All					
		Grade 1					
		Grade 2					
		Grade 3					
		Medical advice					
	Redness (mm)	All					
		≥0.1 - <5.0					
		≥5.0 - ≤20.0					
		>20					
		Medical advice					
	Swelling (mm)	All					
		≥0.1 - <5.0					
		≥5.0 - ≤20.0					
		>20					
		Medical advice					

Dose	Symptom	Type	<each group>			
			N	n	%	95 % CI LL UL
OVERALL/SUBJECT	Pain	All				
		Grade 1				
		Grade 2				
		Grade 3				
		Medical advice				
	Redness (mm)	All				
		≥0.1 - <5.0				
		≥5.0 - ≤20.0				
		>20				
		Medical advice				
	Swelling (mm)	All				
		≥0.1 - <5.0				
		≥5.0 - ≤20.0				
		>20				
		Medical advice				

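### Percentages of doses get a Clopper-Pearson interval that treats an infant's two doses as independent: it is not exact, and it overstates precision if the two responses are positively correlated

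*Protocol*

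**What the plan says.** Each infant is scheduled for "two IM vaccine doses administered according to a 0, 1-month schedule (i.e. at Day 0 and Day 30" (Protocol 3). Protocol 11.8.1 asks for percentages of subjects with an adverse event. It then turns from subjects to doses: "The percentage of doses followed by at least one local AE (solicited and unsolicited", the same for a general event, and the percentage followed "by any AE during the 7-day or 30-day follow-up period will be tabulated, overall vaccination course, with exact 95% CI". The same is asked for each individual solicited event. SAP 6.4.1.1 repeats both requests; the dose percentages "will be tabulated, overall vaccination course, with exact 95% CI".

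The method is named in SAP 11.2: "The exact two-sided 95% CIs for a proportion within a group will be the Clopper-Pearson exact CI". The unit is set in SAP 11.3.2: "The incidence per dose is the number of vaccination visits at which an event was reported among all vaccination visits". The footnotes to Template 17 apply this to the overall/dose row: "N = number of documented dose" and "n/% = number/percentage of doses followed by at least one type of symptom". Templates 16 and 18 to 20 are built the same way. In Templates 55 and 56 the across-dose rows also use documented doses as N with an exact interval.

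None of these sections mentions an adjustment for two observations from one infant.

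**The concern.** Clopper-Pearson inverts a binomial distribution, which needs independent trials. With about 16 infants per group, N in the overall/dose row is about 32; with the minimum of about 8 per group in Steps 1 and 2, it is about 16. Two doses in the same infant share the child, the product, the parent who fills in the diary and preferably the injection site. The two outcomes may well move together.

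If they do, the row holds less information than N suggests. The primary objective is descriptive, so the estimates and their intervals are the main output on reactogenicity. A reader comparing the overall/dose row with the per-subject row would credit the former with precision that the infants in the group may not supply. Templates 55 and 56 add to this: their titles speak of subjects, their combined row counts doses, and they have no overall per-subject row.

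**Working it through.** **Inputs.** Two doses per infant (Protocol 3); m = 16 infants per group at full size and about 8 at the minimum (Protocol 11.4 and Table 1); two-sided 95% Clopper-Pearson (SAP 11.2). The within-infant correlation ρ is in neither document, so it is an assumption and a range is shown.

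**The plan's own figures (subject level).**
- 8 of 16 gives 24.7% to 75.3%, width 50.7 points. Protocol 11.4 says about 50%.
- At least one event at a 10% rate: 1 − 0.9^16 = 81.5% (stated: more than 80%) and 1 − 0.9^48 = 99.4% (stated: more than 99%).

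The documents give no precision figure for percentages of doses.

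**Effect of clustering.** Let X be the number of doses with an event among 2m, with rate p. Then Var(X/2m) = p(1 − p)(1 + ρ)/(2m), and the effective N is 2m/(1 + ρ). For 32 doses from 16 infants, Clopper-Pearson at that effective N gives:

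| ρ | Effective N | Width at observed 50% | Width at observed 25% |
|---|---|---|---|
| 0 (as planned) | 32.0 | 36.2 | 31.9 |
| 0.2 | 26.7 | 39.6 | 35.0 |
| 0.3 | 24.6 | 41.2 | 36.5 |
| 0.5 | 21.3 | 44.2 | 39.2 |
| 1 | 16.0 | 50.7 | 45.1 |

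At ρ = 1 the width ratio is 50.7/36.2 = 1.40.

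**Zero events.** The upper limit is 1 − 0.025^(1/N): 10.9% for N = 32 and 20.6% for N = 16. Under full agreement the dose row would appear to exclude rates that 16 infants cannot exclude.

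**Coverage of the planned interval.** Per infant, P(both doses) = p² + ρp(1 − p), P(exactly one) = 2[p − P(both)], and the remainder is P(neither). The distribution of X is the m-fold convolution. Coverage is the probability of those X whose interval contains p.

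| Infants, ρ | p = 5% | 10% | 20% | 30% | 40% | 50% |
|---|---|---|---|---|---|---|
| 16, ρ = 0 | 98.0 | 98.8 | 97.6 | 96.7 | 95.4 | 98.0 |
| 16, ρ = 0.5 | 95.3 | 96.7 | 93.5 | 91.7 | 89.5 | 94.1 |
| 8, ρ = 0 | 99.3 | 98.3 | 99.3 | 99.0 | 96.3 | 97.9 |
| 8, ρ = 0.5 | 97.5 | 95.8 | 97.6 | 96.0 | 90.6 | 93.7 |

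Coverage is saw-toothed in p, so these round rates are not the whole picture. With 8 infants at ρ = 0.5 it is 90.9% at p = 21%, for example. Averaged over p from 5% to 95%:
- 16 infants: 97.1% at ρ = 0, 95.4% at 0.2, 94.5% at 0.3, 92.5% at 0.5, 87.4% at 1.
- 8 infants: 97.8% at ρ = 0, 95.6% at 0.3, 94.8% at 0.4, 94.0% at 0.5, 89.4% at 1.

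Mean coverage drops below 95% from about ρ = 0.3 with 16 infants and about ρ = 0.4 with 8.

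**The case against.** The deciding input, ρ, is not in the documents. Clopper-Pearson is conservative, and at small ρ this conservatism absorbs the clustering: mean coverage with 16 infants is still 95.4% at ρ = 0.2. At a true rate of 10% with 16 infants it stays at or above 95% up to ρ = 0.8, so rows for rare events may lose little. A slightly negative ρ (−0.1) would make the interval over-cover. All of this stands. A reader might infer that the overall/dose intervals are always too narrow, or that groups of 8 fare worst. The documents do not support the first, and the enumeration contradicts the second: under equal correlation, mean coverage is higher with 8 infants than with 16.

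The rows also carry no decision. The holding rules in Protocol 9.10.5 count infants per group, the between-group comparison in Protocol 11.8.2 uses percentages of subjects, and SAP 7 calls all analyses descriptive. The Dose 1 and Dose 2 rows, where each infant counts once, address the endpoint after each vaccination directly. So a reader who concluded that the primary safety assessment is compromised would be going too far.

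These points limit the consequence but do not rescue the label. For any ρ above 0 the interval is narrower than the matching clustered one, and nothing in the design makes ρ zero.

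**Conclusion.** The point holds as a reporting fault. The overall/dose rows (Templates 16 to 20) and across-dose rows (Templates 55 and 56) carry an interval labelled exact that is not exact for two doses per infant. Whether it is materially too narrow depends on a correlation that has to be assumed. At ρ = 0.5 the loss is moderate: at the rates tabulated, coverage is at worst 89.5% with 16 infants and 90.6% with 8, and it stays above 95% at 5 and 10%. The contrasts of 51 against 36 points and of 20.6% against 10.9% require ρ = 1 and are the bound, not the expected case. Dose 1, Dose 2 and correctly defined per-subject rows, the holding rules and the between-group comparisons are unaffected.

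**What to change.** In Protocol 11.8.1 and SAP 6.4.1.1, show percentages of doses without a confidence interval. If an interval is wanted, use one that allows for clustering and still gives an upper limit when there are no events. A simple conservative choice is Clopper-Pearson with N set to the number of infants and the count set to N times the observed percentage; the beta-quantile form accepts half counts. A percentile bootstrap by infant is unsuitable: with no events it returns 0% to 0%, and zero cells are likely in groups of 8 to 16.

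Keep the exact intervals for Dose 1, Dose 2 and per-subject rows. Add an overall per-subject row to Templates 55 and 56, and retitle or relabel their across-dose row so that it is clear that doses are counted. Because the reader will then rely on the per-subject rows, also correct the footnotes of Templates 16 and 18, which define the overall/subject N as documented doses where Templates 17, 19 and 20 use subjects.

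The cost is a few sentences in the SAP, matching protocol wording and a small programming change. The dose-level intervals become wider or disappear; no data collection, holding rule or group comparison changes.

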11.8.2. Between groups assessment

Exploratory comparisons between the investigational RSV groups and the Placebo groups will be done in terms of the percentage of subjects, overall doses, reporting any Grade 2/3 AE during the 7-day follow-up period (Day 0-6) after vaccination, and/ or any fever >38.5°C during the 7-day follow-up period (Day 0-6) after vaccination, and/ or any vaccine-related SAE during the 7-day follow-up period (Day 0-6) after vaccination.

The standardized asymptotic 95% CI for the difference between the RSV groups and (minus) the Placebo groups will be computed.

11.9. Analysis of immunogenicity

The primary analysis will be performed on the ATP cohort for immunogenicity and, if in any group the percentage of vaccinated subjects with serological results excluded from the ATP cohort for analysis of immunogenicity is more than 10%, a second analysis will be performed on the TVC.

11.9.1. Within groups assessment

11.9.1.1. Analysis of secondary objectives

The following parameters will be summarized by group using descriptive statistics, at each timepoint during which blood samples are collected for CMI in investigational sites with a laboratory in proximity capable to perform WBS necessary for the CMI assay:

- Frequency of CD3+/CD4+ T-cells expressing at least two markers among CD40L, IL-2, TNF- α , and IFN- γ upon stimulation with F, N and M2-1 peptide pools.

For each group, at each timepoint that blood samples are collected for humoral immune response against the investigational RSV vaccine (neutralizing antibody titers against RSV-A, RSV F antibody concentrations, and palivizumab-competing antibody concentrations):

- GMTs/GMCs will be tabulated with 95% CI and represented graphically.
- Percentage of subjects above the seropositivity threshold will be tabulated with exact 95% CI.
- Antibody titers/concentrations will be displayed using reverse cumulative curves.

- The distributions of neutralizing antibody titers/concentrations will be tabulated.
- Percentage of responders in terms of neutralizing antibody titers will be tabulated with exact 95% CI.
- Individual post-vaccination versus pre-vaccination results will be plotted using scatter plots. Results of the Placebo groups will be used as a reference.
- Geometric mean of ratios of antibody titers/concentrations at each post-vaccination timepoint over pre-vaccination will be tabulated with 95% CI.
- Distribution of the fold increase of the neutralizing antibody titers will be tabulated by pre-vaccination titer category.
- The kinetics of individual antibody titer/antibody concentration results will be plotted as a function of time for subjects with results available at all timepoints.

11.9.1.2. Analysis of tertiary objectives

The cellular immune response will be further characterized using descriptive analysis of the frequency of CD3+/CD8+ T-cells and CD3+/CD4+ T-helper cell profile (Th1, Th2, Th17) expressing at least one or any combination of marker(s) among IL-2, CD40L, 41BB, TNF- α , IFN- γ , IL-13, and IL-17.

If available, any further exploratory immunology results (including, but not limited to anti-vector immunity) will be reported by group and timepoint using descriptive summary statistics.

11.10. Analysis of RTI and LRTI

The analysis will be performed on the TVC on two pooled groups (i.e. pooled RSV and pooled Placebo) separately for first and second RSV seasons and overall.

The proportion of subjects with at least one RSV-associated RTI (with 95 % CI) will be calculated. The same descriptive analysis will be performed for subjects with at least one RSV-associated LRTI and those with at least one RSV-associated severe LRTI.

As primary analysis, the assessment of RSV infection will be performed using the quantitative RT-PCR according to standardized case definitions (see [Table 4](#)) based on the available WHO case definitions.

Descriptive analyses (mean, median, min, max) of viral load assessed by the quantitative RT-PCR (RSV-A/B) of RSV-RTI, RSV-associated LRTI and severe LRTI cases will be tabulated. This analysis will also be done by study group.

The incidence rate of all-cause RTI (with 95% CI) will be calculated by group. The same descriptive analysis will be performed for all cause LRTI and all cause severe LRTI. These will also be presented for each viral etiology identified by multiplex PCR.

The incidence rate of asymptomatic RSV infections (with 95% CI) detected by the quantitative PCR (RSV-A/B) will be tabulated by group. Descriptive analyses (mean,

median, min, max) of viral load assessed by the quantitative RT-PCR (RSV-A/B) of those asymptomatic RSV infections will also be done by group.

11.11. Interpretation of analyses

Comparative analyses will be exploratory and should be interpreted with caution considering that there is no adjustment for multiplicity and that group sizes are small for these comparisons.

